9.4. Safety Monitoring Plan

CPI will perform the clinical data and safety monitoring. TPI from I2R will perform the fMRI data and safety monitoring. Daily review of any possible adverse events such as medical adverse events, allergic reactions to the accelerometers' straps, adverse events of fMRI investigations.

Refer to Section 9 Safety Measurement to understand the plan in place to ensure the safety and well-being of the subjects.

Refer to 10.1 Data Quality Assurance to understand how integrity of data collected will be ensured.

9.5. Complaint Handling

CPI will handle complaints in consultation with TPI. If the data of complainants will still be used for analysis unless specified by the complainants not to be included in this study.

10. DATA ANALYSIS

10.1. Data Quality Assurance

CPI will check the data of all clinical assessments and TPI will check on the data of fMRI investigations to ensure that the data obtained from this research is accurate, complete and reliable. Reviews will be performed daily.

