20 eligible stroke subjects with positive motor evoked potential (MEP +ve) and with severe to moderate UL paresis (ULFM score below or equal to 50) admitted to TTSRHC will be selected. Subjects with severe and moderate UL paresis are selected because based on clinical observation subjects with this level severity require intensive UL practice to improve their UL functions, while subjects with mild paresis do not require such high intensity of UL practice for significant improvement. Investigation of motor evoked potential on extensor carpi radialis on the affected hand will be performed on stroke patients at NUH using a single Magstim 200 to prognosticate recovery. Subjects with MEP +ve will be selected to ensure that all the subjects chosen in this study have intact ipsilesional cortical spinal tract function to make comparison of UL

recovery more consistent.

d. Rationale for Study Design

Randomized blinded controlled trial study design has been selected for this study to investigate whether if **SURE** program improves UL functional outcome and influences neuroplasticity positively to optimize UL recovery after stroke. This study design is chosen to prevent any bias in the assessment of outcomes.

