5. STUDY DESIGN

Experimental procedure

The subjects will be randomly assigned to a control (N=10) and experimental group (N=10).

Experimental Group

The experimental group will receive one **SURE** program booklet with specific instructions and pictorial illustrations of each exercise and functional use according to their affected ULFM score. There are 3 booklets available (Level 1A for patients with affected ULFM score from 0 to 10; Level 1B for patients with affected

ULFM score from 11 to 22; Level 2 for patients with affected ULM score from 23 to 50). Each **SURE** program booklet consists of stretching exercises, strengthening exercises and performance of simple motor tasks such as reaching, picking up cubes etc. Each exercise will be graded and progressed according to the subjects' affected UL capability by the Clinical Principal Investigator (CPI) who is an experienced principal physiotherapist. The **SURE** program booklet also consists of selected motor tasks to be performed by the subjects using their affected UL. Functional activities such as subjects will be using their affected UL to wipe their faces; wiping the table after eating; applying lotion by the affected hand along the unaffected arm and legs after shower; drinking water from cup/ bottle; lifting and placing affected hand on table top; etc. Each functional motor task will be selected, graded and progressed by the PI according to the subjects' affected UL motor capability during the reviews. The subjects will be taught how to perform the exercises and functional tasks during the first session. The performance of the exercises and functional motor tasks will be reviewed by the CPI three times per week for the first 2 weeks, two times for the third week and one time for the fourth week of intervention period.

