The subjects will be asked to perform the exercises 60 minutes (3x 10- 20 minutes) distributed across morning, afternoon, and evening per day for 6 days per week during the 4-week intervention period. They will also be asked to perform the functional tasks as and when is required for their daily function for 6 days per week during the 4-week intervention period. The subjects will be given an Exercise Log to tick and track number of repetitions of the exercises and functional activities each day, the number of days the protocol is completed, and the level of fatigue and pain experienced. If the subject is discharged from the hospital before the 4 weeks of intervention period, he/ she has to carry on with the protocol till the intervention period ends. The CPI will continue to review exercises and the amount of affected UL use with the subjects at home if the subjects are discharged till the intervention period ends.

Control Group

The control group will receive an education booklet with 10 modules. The education booklet will contain information on stroke, recovery and management strategies after stroke. Subjects are to complete 2-3 modules per week and answer 1-2 simple questions after each module. Each module including answering questions takes approximately 5-10 minutes to complete. The CPI will review the information with the subjects 3 times per week for the first 2 weeks, two times for the third week and one time for the fourth week of intervention period.

Both groups will continue with their daily routine therapy sessions in the hospital. The treating therapists will record the duration of therapy of each subject per day.

UL functional outcome measures- ULM and ARAT will be assessed pre-intervention, 2 weeks after start of intervention, post-intervention, 1month and 3months post-intervention. Measures of **SURE** program's feasibility such as VAS pain score, fatigue level, and MAS of biceps and finger flexors will be measured pre-intervention, 2 weeks after start of intervention and post-intervention. A team member who is blinded to which group the subjects are in will perform the outcome measure assessments.

Multimodal imaging for the normal healthy control will be performed once to establish the activation pattern in normal. Multimodal imaging assessment for the patient subjects will be done pre-intervention, post-intervention, and 3months post-intervention.

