6.1. Randomisation and Blinding

Random assignment of subjects will be done using the randomizer found in the web (www.Randomizer.org/form.htm). A non-team member will generate the randomized allocation sequence, seal the group numbers in individual envelopes, and arrange them according to the randomized allocated sequence. These envelopes will be kept under lock and key in TTSRHC. The same non-team member will pass these sealed envelopes in accordance to the randomized allocated sequence one at a time to the CPI who will enrol and assign the eligible subjects to their groups. The unmasking of the randomization will be at the end of data collection and fMRI analysis. A blinded assessor will perform all the clinical assessments. The I2R who will be performing the fMRI analysis will be blinded to the group which the subjects are in.

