On the day of travel, the CPI will check with the treating doctor if the subject is clinical fit to travel, if the doctor deems the subject clinically unfit to travel, the ambulance services and TMS/ fMRI will be cancelled for that day and the subject will remain in the ward and not travel. If the doctor deems the subject clinically stable to travel, the subject will be accompanied by CPI and paramedic in the ambulance service to NUH and CIRC.

In the process of transportation, if the subject suffers any adverse events or re-stroke, the paramedic accompanying the subject in the ambulance will manage the emergency situations and send the subject to the nearest hospital Emergency Department. The CPI will call the treating doctor in TTSHRC to inform and update on the emergency situation and subject's location. The CPI will stay with the subject until further instructions has been given by the treating doctor in TTSHRC.

c. *Final Study Visit:*

The final study visit will be either the three-months post-intervention clinical assessment or fMRI investigation.

d. *Post Study Follow up and Procedures*

CPI will check on all clinical assessments and TPI will check on all fMRI investigations to ensure that all the assessments and investigations are done accurately and the results obtained are accurately. CPI and TPI will also check and monitor for any adverse events occurring during **SURE** program and fMRI investigations.

e. *Discontinuation Visit and Procedures*

All clinical assessments and fMRI investigations should be done until the subject indicate to the CPI that he/she want to withdraw voluntarily from participation in the study at any time. Subjects may also withdraw voluntarily from receiving the **SURE** program for any reason. All the withdrawals and reasons for withdrawal will be evaluated to gain an insight to the feasibility of SURE program. As **SURE** program is a safe exercise program, no efforts will be made to follow-up if the subject chooses to withdraw from the program, unless subject has specifically requested for follow-up.

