8.5. Blinding

The therapists performing the clinical assessments, the I2R and CIRC scientists performing the fMRI investigations and analysis will be blinded to which group the subjects are in. Only the CPI and another team member who will be carrying out the **SURE** program when PI is unavailable will know which group the subjects are in. The subjects will not be told which group they are in as well. The **SURE** program and education program will be delivered to them without disclosing which group they are in. The unblinding is expected and will only occurs after all the clinical assessments and fMRI investigations are completed for individual subjects.

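### An unblinded CPI is charged with checking the accuracy of the observer-rated primary outcomes, and no safeguard is stated around that check

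*Protocol*

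**What the plan says.** **The check.** Section 10.1 (Data Quality Assurance) says that the "CPI will check the data of all clinical assessments", the aim being accurate, complete and reliable data. It adds: "Reviews will be performed daily". Section 6.3d gives the same duty: "CPI will check on all clinical assessments and TPI will check on all fMRI investigations to ensure that all the assessments" and investigations are carried out accurately and give accurate results. Section 9.4 also makes the CPI the monitor of clinical data and safety.

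**The CPI's other roles.**
- Section 6.1: sealed envelopes are passed "one at a time to the CPI who will enrol and assign the eligible subjects to their groups".
- Section 5, experimental arm: performance of the exercises and functional tasks "will be reviewed by the CPI three times per week for the first 2 weeks", with fewer reviews after that.
- Section 5, control arm: "The CPI will review the information with the subjects 3 times per week for the first 2 weeks", on the same declining schedule.
- Section 8.5, on who knows the allocation: "Only the CPI and another team member who will be carrying out the" SURE program when the principal investigator is not available.

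**What the design relies on.** Section 1.2d says of the randomised blinded design: "This study design is chosen to prevent any bias in the assessment of outcomes". Sections 5, 5.1, 6.1 and 8.5 give the clinical scoring to blinded assessors. Section 6 names ULFM and ARAT as primary outcome measures.

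**The concern.** A blinded assessor protects a score only while nobody who knows the group can influence it before it is final. ULFM and ARAT are observer-rated, so a question about whether a score is accurate can reopen a judgement and need not stop at a missing field or a transcription slip. If questions are raised more often when a score looks surprising for the known group, the checking is differential even when every question is honest. The pattern of questions could also hint at allocation to the assessor.

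At stake is whether the between-group comparison of ULFM and ARAT can be reported as based on blinded assessment all the way to the final data. The trial is a pilot, but section 11.2 still tests group differences at the 0.05 level with 10 subjects per arm.

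**Working it through.** No figure in the protocol is in dispute, so the check is a tracing of roles plus one count.

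**1. Who knows the allocation?** Section 8.5 names two people: the CPI and the team member who covers SURE delivery. Section 6.1 has the CPI make the assignments, and section 5 has the CPI in regular contact with both arms. The CPI is therefore unblinded by design.

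**2. Who makes the primary scores?** A blinded assessor does (sections 5, 5.1, 6.1). Section 8.5 refers to the assessing therapists in the plural, so more than one blinded person appears to exist.

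**3. Who checks the scores, and for what?** The CPI does (sections 6.3d, 9.4, 10.1). Section 6.3d asks that the assessments be done accurately and that the results be accurate. That reaches the score itself and is wider than completeness of the form.

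**4. What limits the check?** Sections 6.1, 6.3, 8.5, 9.4, 10.1 and 10.2 state no point at which a score becomes final before the CPI sees it, no rule on who may correct it, no record of corrections and no blinded second checker. Section 10.2 puts clinical data on paper and makes access subject to the CPI's permission.

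**5. How does imaging compare?** Imaging data are checked by the TPI, who is from I2R (sections 9.4, 10.1). Sections 6.1 and 8.5 state that the I2R analysts are blinded. So the imaging check sits with a group described as blinded, while the check on the clinical primary outcomes sits with an unblinded person.

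**6. How many records are exposed?**
- Subjects: 20 (section 3.1).
- Visits: 5, namely pre-intervention, 2 weeks, post-intervention, 1 month and 3 months (section 4). Leaving out pre-intervention gives 5 - 1 = 4.
- Primary scales: 2.
- Post-baseline primary records: 20 x 4 x 2 = **160**.

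The 20 x 2 = 40 baseline records are left out because the CPI needs baseline ULFM to choose the booklet (section 5).

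**The case against.** The strongest reply is that scoring stays with a blinded assessor and that the CPI is given only a duty to check. No section lets the CPI alter a score, return it or ask for a re-rating. Rules for queries and corrections often sit in data-management procedures outside the protocol, and investigator oversight of data quality is ordinary in a 20-subject pilot sized on feasibility (section 11.1).

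Much of this stands. It rules out several stronger readings that a reader might infer:

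- *That the CPI can change scores, or that bias has been shown.* The text supports neither. It shows an unguarded step and no more.
- *That the CPI alone knows the allocation, or controls the sequence.* Section 8.5 names a second person. Section 6.1 has a non-team member generate the sequence and seal the envelopes.
- *That every outcome score is reviewed daily.* Daily is a general review frequency covering clinical and imaging data together. The clinical outcomes are collected at only five visits.
- *That the imaging side is fully protected.* The TPI's own blinding is inferred from membership of I2R, and section 10.2 gives the CPI access to fMRI data as well.
- *That a shift in points can be put on the bias.* The protocol gives nothing from which to derive one, and the planned test in section 11.2 is rank-based, so a shift in an arm mean is not the quantity tested.

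The reply does not remove the point. The protocol itself assigns the accuracy check to an unblinded person, in three sections. The concern is with that stated assignment and does not depend on detail left to another document.

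**Conclusion.** The point holds as a weakness in role separation. An unblinded CPI is responsible for the accuracy of 160 post-baseline primary-outcome records, and nothing stated keeps knowledge of the group from influencing them after scoring. This leaves open a route to bias that the blinded-assessor design in section 1.2d is meant to close.

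The conclusion assumes that the accuracy check extends to the scores themselves, as the wording of section 6.3d suggests, and that all 20 subjects attend all four post-baseline visits. Whether bias would occur, and how large it would be, cannot be determined from the document. The point is worth acting on because the remedy is cheap.

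**What to change.** In sections 10.1 and 6.3d, with section 9.4 brought into line, state that:

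1. Post-baseline ULFM and ARAT scores are finalised by the blinded assessor before the CPI sees them.
2. Their accuracy check is done by an existing blinded team member. This cannot be the second SURE deliverer, who knows the allocation, and should preferably not be the assessor who made the score.
3. Any correction is made, dated and initialled only by the blinded assessor.

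The CPI keeps access to pain, fatigue and MAS data and to adverse events. Section 2.4b uses the fatigue scale as added safety monitoring and section 9.4 makes the CPI the clinical safety monitor, so withholding those data would conflict with the protocol. The CPI also keeps baseline ULFM for booklet choice.

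The change is to protocol wording and to who does an existing task; no new staff or visits are needed. The downside is slightly slower query handling. It protects only scores that the CPI has not yet reviewed, so it should be made before post-baseline checking begins.

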10.2. Data Entry and Storage

Data from clinical assessments will be entered on paper. Soft copy of the research data will be stored in research staff's computers, laptops and portable hard disks. All the research staff involved in the investigation will use password protected laptops and PCs for development and study. The subjects' identifiers will be coded and be stored separately from the research data. The original personal data will only be accessed by the CPI. The data can only be accessed with the permission from the CPI. The CPI's personal computer and laptop are protected by password. The hard disk and hard copy of the data will be kept in a secure cupboard in TTSHRC. The anonymized data will only be available to CO-Is and related research personnel involved in the study.

Data from fMRI investigations will be entered electronically. CPI, TPI, I2R scientists, CIRC scientists will have accessed to fMRI data. The data will be stored in a secured server (I2R), which is in a locked room and the data can only be accessed by password.

11. SAMPLE SIZE AND STATISTICAL METHODS

11.1. Determination of Sample Size

Since this study is a pilot exploratory trial, results of individual subjects from each group will be analysed in

detail to determine the difference in brain neuroplasticity between the control and experimental groups. N=10 from each group is chosen because it is deemed feasible to recruit stroke patients who will be willing to participate in this study clinically in the period of 2 years (the time period of the funding).

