2.2. Primary Objectives

To investigate the effectiveness of SURE program to increase UL practice in the ward and improve UL functional outcomes after stroke. To correlate the imaging biomarkers with the neuro-recovery outcomes under SURE and controlled program.

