3. STUDY POPULATION

3.1. List the number of subjects to be enrolled.

20 subjects will be randomly assigned to a control (N=10) and experimental group (N=10). 4 normal healthy subjects will also be recruited for fMRI investigations.

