5.1. Summary of Study Design

The subjects will be randomly assigned to a control (N=10) and experimental group (N=10). The control group will undergo an education program while the experimental group will undergo the **SURE** program. Clinical assessments for both groups will be performed by a blinded assessor at pre, two weeks after start of intervention, immediate post intervention, 1 and 3months post-intervention to determine if the **SURE** program improve affected UL functional outcomes compared with the control group. fMRI investigations will be performed at pre-intervention, post- intervention and 3months post-intervention to determine if the increased UL activity in the **SURE** program influences brain neuroplasticity positively early post-stroke.

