11.2. Statistical and Analytical Plans

a. Study Statistical Analysis

Statistical analysis will be performed using STATA version 10.0 for Windows (StataCorp, TX, USA). Descriptive statistics will be used to describe subjects' demographics in each group.

Analysis of UL Functional Outcome

Wilcoxon signed-ranked tests will be used at each time points (pre, 2 weeks after start of intervention, post, 1month post-intervention, 3months post-intervention) to compare UL functional outcomes between the experimental and control groups. The significance level for all statistical tests will be set at $p<0.05$ levels. All data will be analysed by intention to treat.

Analysis of feasibility of accelerometers to measure affected UL use

Analysis of the compliance rate and responses from the questionnaire will be used to determine the feasibility and acceptance of using accelerometers to measure affected UL use after stroke.

Analysis of SURE Program's feasibility

Wilcoxon signed-rank test will also be used to compare outcomes of pain, fatigue and spasticity pre-and post-intervention period. The differences in the duration of affected UL use per day and the ratio of affected UL use/ non-affected UL use between the experimental group and control group (from the accelerometer recordings), the rate of compliance, the proportion of subjects who successfully complete the whole training, and the dropout rate will be calculated to assess the feasibility of **SURE Program**.

Analysis of fMRI investigation

Comparison of activation in primary motor cortex, secondary motor cortex and cerebellar hemisphere for bilateral sides will be done by comparing mean percentage signal change (%SC), absolute voxel counts (VC) and changes in geometric centers of these areas on both sides¹⁷. In addition, a laterality index (LI) will also be calculated to determine the relative cortical activity. Asymmetry has been found to restore to normal (L=1.0) when the affected hand movement improved after rehabilitation⁴¹.

Analysis of resting state fMRI/DTI

Functional connectivity and tract integrity^{32,38} will be studied by FSL with the normalization method^{39,40}. The secondary degeneration of the brain in the remote region to the primary lesion will also be studied for the sub-groups of subjects with less motor recovery³⁰.

MRS analysis

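### A pilot sized by recruitment feasibility is set to determine effectiveness by p<0.05 tests, which 10 per group cannot settle; the effect should be estimated with an interval

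*Protocol*

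**What the plan says.** Protocol Section 11.1 gives the trial's status, "Since this study is a pilot exploratory trial", and the only basis for its size: "N=10 from each group is chosen because it is deemed feasible to recruit stroke patients" within the two-year funding period. It states no effect size, SD or power. The analysis aim it ties to the pilot status is a detailed look at individual results for a difference in neuroplasticity; it does not mention ULFM, ARAT or arm use.

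Elsewhere the purpose is wider. Section 2.2 opens: "To investigate the effectiveness of SURE program to increase UL practice in the ward and improve UL functional outcomes after stroke". Section 5.1 says the blinded assessments are made to determine if the SURE "program improve affected UL functional outcomes compared with the control group". Section 6 names both ULFM and ARAT as primary outcome measures.

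Section 11.2 compares these outcomes between groups with a Wilcoxon signed-rank test at each of five time points, and adds a general rule: "The significance level for all statistical tests will be set at" p<0.05. It names no other analysis for ULFM or ARAT. For accelerometry, under the feasibility heading, it says that "The differences in the duration of affected UL use per day" and in the ratio of use between groups will be calculated. No measure of uncertainty is attached.

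**The concern.** The stated design is exploratory, but the stated method of judging the primary outcomes is confirmatory in form: a test against 5%, serving a section that asks whether the program works. The two do not fit. A test with 10 patients per arm answers a yes/no question poorly in both directions. If it is not significant, a reader of Section 5.1 may take the question as answered in the negative when the data are compatible with a useful benefit. If it is significant, the observed difference has passed a high threshold and will tend to be larger than the truth, which matters if it is later used to plan another study.

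For arm use, the other half of the effectiveness objective, a bare difference between two groups of 10 cannot be told from chance.

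The choice of 10 per group is not in question here. Feasibility is an acceptable basis for a pilot.

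**Working it through.** The protocol has no power calculation to reproduce. The check is therefore what 10 v 10 can show.

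**Inputs from the protocol:** 10 per group (Sections 3.1, 5 and 11.1); significance level 0.05 for every test (11.2); ULFM entry range 0 to 50 (3.3, 5); 60 minutes of prescribed exercise per day (5, 8.1).

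**Assumptions:** two-sided tests (sidedness is not stated); a rank-sum test for independent groups, because the signed-rank test named in 11.2 is for paired data (a separate error); normal outcomes with equal SD; true effects in SD units, as the protocol gives none.

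**Precision.** Unadjusted 95% CI half-width = t(0.975, 18 df) × sqrt(1/10 + 1/10) = 2.101 × sqrt(0.2) = 0.94 SD. An observed difference of 0.5 SD would give an interval from 0.5 − 0.94 = −0.44 SD to 0.5 + 0.94 = 1.44 SD.

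**Power and overstatement.** Rank-sum power comes from 8,000 simulated trials per row. Overstatement is the mean size of the significant differences divided by the true effect (t-test, 40,000 simulated trials per row).

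| True effect (SD) | Rank-sum power | Overstatement if significant |
|---|---|---|
| 0.3 | 8% | 3.5 times |
| 0.5 | 16% | 2.2 times |
| 0.8 | 36% | 1.5 times |
| 1.0 | 51% | 1.3 times |
| 1.2 | 67% | 1.2 times |
| 1.32 | 76% | 1.1 times |

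A second simulation of 20,000 trials per effect gave 16.1% at 0.5 SD, 35.2% at 0.8 SD and 80.1% at 1.4 SD. The overstatement arises because, by t-test, an observed difference must exceed about 0.94 SD to reach significance.

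**In ULFM points (illustration only).** For an assumed SD of 10 to 18, the half-width is 0.94 × 10 = 9 points to 0.94 × 18 = 17 points. A uniform spread over the entry range would give SD = 50/sqrt(12) = 14.4 and a half-width of 13.5 points. That spread describes entry scores; follow-up scores are not capped at 50.

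**Arm use (illustration only).** Standard error of the difference = SD × sqrt(0.2). For an assumed between-subject SD of 30 to 90 min/day, this is 30 × 0.447 = 13 to 90 × 0.447 = 40 min/day, against 60 prescribed.

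**What baseline adjustment could gain.** With one covariate, half-width = t(0.975, 17 df) × sqrt(0.2) × sqrt(1 − r²) = 2.110 × 0.447 × sqrt(1 − r²). For an assumed baseline correlation r of 0.7 this is 0.67 SD, and for 0.8 it is 0.57 SD.

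**The case against.** The best defence has four parts.

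- **Choice of estimator and intervals is usual SAP content, and the SAP is not shown.** This stands as far as it goes: a missing interval alone would be no finding, and Section 11.2 does not say that only p-values will be reported. What a SAP would not remove is the mismatch within the protocol between the stated status and size in 11.1, the purpose in 2.2 and 5.1, and the test in 11.2.
- **The wording conflict is narrow.** Only Section 5.1 uses the verb determine for arm function. Section 2.2 says investigate, which suits exploratory work, and the aims in Section 1.2 pair effectiveness with feasibility. This also stands. But Section 2.2 drops feasibility from the formal primary objective, and the only inference stated for the primary outcomes is a significance test.
- **Section 11.2 does plan an estimate for arm use**, as a feasibility measure, where description is reasonable. Correct. The remaining point is that Section 2.2 also places increased practice in the primary objective, so the difference needs a measure of its uncertainty.
- **An interval does not shrink an inflated point estimate.** True, but the inflation comes from selecting on significance. Reporting the estimate whatever its p-value removes that selection.

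A reader might go further and infer that the sample size is wrong, or that the sponsor will report p≥0.05 as no effect and p<0.05 as proof. The protocol supports neither: a feasibility-based pilot is legitimate, and no section states such a reading of the results.

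**Conclusion.** The point holds as a mismatch between stated design and stated method. At 10 v 10, a two-sided 5% test has about 16% power at 0.5 SD and 35% at 0.8 SD, and the unadjusted 95% interval is about ±0.94 SD. A non-significant result would therefore be inconclusive for moderate effects, and a significant one would tend to overstate a true effect below about 1 SD.

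It would be too strong to call a null result uninformative or a significant one inflated without condition. Near 1.3 SD the overstatement is only about 1.1 times, and baseline adjustment could narrow the interval appreciably. The half-width in SD units follows from the group sizes and the usual equal-variance assumption. The power and overstatement figures rest on assumed effects and an independent-groups test, and the point and minute figures on assumed SDs.

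The change is worth making: it alters what the trial can properly conclude, at almost no cost.

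**What to change.** - **Section 11.2, ULFM and ARAT:** make the between-arm difference with its 95% CI the main reported result, either baseline-adjusted with the pre-intervention score already collected or as a Hodges-Lehmann estimate. Keep p-values as secondary.
- **Section 11.2, arm use:** attach a 95% CI to the difference already planned.
- **Section 5.1:** restate the purpose as estimating the effect of SURE on arm function, and align Section 2.2 with it.
- **Section 11.1:** state that the trial is not sized to conclude for or against effectiveness.

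The cost is a more modest claim and slightly more output per outcome. No additional patients, visits or data are needed.
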